12.2 Phase I Sample Size/Accrual Rate

As previously stated, the rolling-6 design will be applied. The minimum sample size of four occurs in the case that the first two patients on dose level 1 have a DLT, the dose is reduced and then the first two patients on dose level -1 have a DLT. The maximum sample size of 24 patients occurs if 6 patients are treated at each of the 4 dose levels. Thus, the total sample size may be as small as 4 and as large as 24 evaluable participants. The principal investigator estimates an annual accrual of 10 to 12 patients per year.

12.3 Phase II Sample Size/Accrual Rate

For purposes of this Phase II evaluation, we define a success as complete remission, complete remission with incomplete count recovery, or, for patients who are enrolled with <5% blasts, the achievement of MRD negativity, by the end of one course of therapy. Patients who die before reaching this milestone will be counted as failures for purposes of this Phase II design. We will use Simon's minimax two-stage design for the Phase II component.²² In the first stage, we will enroll 28 patients. Patients who have been enrolled on the dose expansion cohort and who meet the eligibility criteria for the Phase II portion of the study, will be included in the analysis. The study will stop at any point it becomes impossible to obtain 8 or more successes (CR or CRi or MRD negativity) among the first 28 patients. If 8 or more successes are observed among the first 28 patients, the study will continue to enroll an additional 11 patients for a total of 39 patients. For the phase I portion of the trial, we enrolled 18 patients in 15 months, for an accrual rate of 1.2 patients/month. Conservatively assuming each of the four additional participating sites enroll one patient per year, the accrual will increase to 1.5 patients/month. At this rate the study will be open for as little at 19 months or up to as long as 26 months.

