Appendix I: Selinexor Dose Rounding Chart

Appendix II: Performance Status Criteria

Appendix III: Tests Performed for Routine Care and for Research

Appendix IV: Selinexor Dose Modification Guidelines for AEs Associated with Selinexor

Appendix V: Specimen Submission Guidelines

1.0 OBJECTIVES

1.1 Primary Objective

- 1.1.1 To determine a tolerable combination of selinexor, fludarabine, and cytarabine in pediatric patients with relapsed or refractory hematologic malignancies including acute myeloid leukemia (AML), acute lymphoblastic leukemia (ALL), mixed phenotype acute leukemia (MPAL) and myelodysplastic syndrome (MDS) in the phase I portion of the study.
- 1.1.2 To estimate the overall response rate, as defined by complete response or complete response with incomplete count recovery, of selinexor in combination with fludarabine and cytarabine for patients with relapsed or refractory AML in the phase II portion of the study.

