3.0 ELIGIBILITY CRITERIA AND STUDY ENROLLMENT

3.1 Inclusion Criteria

According to institutional and NIH policy, the study will accession research participants regardless of gender and ethnic background. Institutional experience confirms broad representation in this regard.

- 3.1.1 **Phase I (completed)**: Participants must have a diagnosis of AML, MDS, ALL or MPAL and must have disease that has relapsed or is refractory to chemotherapy, or that has relapsed after hematopoietic stem cell transplantation (HSCT)
- a) Refractory disease is defined as persistent disease after at least two courses of induction chemotherapy.
 - b) Patients with AML, MPAL or MDS are eligible at first or subsequent relapse, whereas patients with ALL are eligible at second or subsequent relapse or any relapse that is refractory to salvage chemotherapy.
 - c) Patients with AML or ALL must have $\geq 5\%$ leukemic blasts in the bone marrow or increasing levels of MRD in the bone marrow as assessed by flow cytometry. If an adequate bone marrow sample cannot be obtained, patients may be enrolled if there is unequivocal evidence of leukemia in the peripheral blood.
- 3.1.2 **Phase II**: Participants must have a diagnosis of AML and must have disease that has relapsed or is refractory to chemotherapy, or that has relapsed after hematopoietic stem cell transplantation (HSCT)
- Refractory disease is defined as persistent disease after at least two courses of induction chemotherapy.
 - Patients are eligible at first or subsequent relapse or any relapse that is refractory to salvage chemotherapy.
- 3.1.3 Patients must have $\geq 5\%$ leukemic blasts in the bone marrow and/or increasing levels of MRD in the bone marrow as assessed by flow cytometry. If an adequate bone marrow sample cannot be obtained, patients may be enrolled if there is unequivocal evidence of leukemia in the peripheral blood.
- 3.1.4 Adequate organ function defined as the following:
- Direct bilirubin ≤ 1.5 x institutional upper limit of normal (IULN)
 - AST (SGOT)/ALT (SGPT) < 3 x IULN
 - Creatinine within normal institutional limits for age
- 3.1.5 Prothrombin time (PT) and partial thromboplastin (PTT) ≤ 1.5 x IULN.
- 3.1.6 Age criteria: Patients treated at collaborating sites and current St. Jude patients who are on therapy or within 3 years of completion of therapy must be ≤ 24 years old. All other St. Jude patients must be ≤ 21 years old.
- 3.1.7 Patients must be able to swallow tablets.

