4.0 TREATMENT PLAN

4.1 Overview

Patients must have fully recovered from the acute effects of all prior therapy before starting selinexor. In addition, at least 14 days must have elapsed since the completion of myelosuppressive therapy or gemtuzumab ozogamicin and the first dose of selinexor. At least 24 hours must have elapsed since the completion of low-dose or non-myelosuppressive therapy, such as hydroxyurea, vincristine, steroids, or low-dose cytarabine (up to 100 mg/m²/day), and the first dose of selinexor. For patients who have received prior HSCT, there can be no evidence of GVHD and greater than 60 days must have elapsed since the HSCT.

This study will include two phases. The dose-escalation phase will characterize the dose-limiting toxicities (DLTs) and determine the maximum tolerated dose (MTD) and recommended phase 2 dose (RP2D) of selinexor when given in combination with fludarabine and cytarabine. The RP2D will be chosen based on the MTD and totality of the data (clinical, PK, and PD data from this and other trials). The phase II cohort will further assess the safety and will explore the efficacy of this combination.

Selinexor will be given orally on days 1, 3, 8, 10, 22 and 24 of each cycle.

Fludarabine (30 mg/m²/dose IV over 30 minutes daily) and **cytarabine** (2 gram/m²/dose IV over 4 hours daily) will be given on days 16 (\pm 2 days) through 20 (\pm 2 days). Chemotherapy may be delayed if clinically indicated.

For patients who achieve CR or CRi with negative MRD or with MRD that has decreased at Day 15, the treating physician may continue single agent selinexor without fludarabine and cytarabine. In this case, selinexor should be given on days 1, 3, 8, 10, 15, 17, 22 and 24.

Patients who achieve CR or CRi status (as defined in Section 8.1) at day 15 (regardless of MRD status) may proceed directly to HSCT at the discretion of the treating physician.

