8.1.1 Complete remission (CR)

- Bone marrow with < 5% blasts confirmed by flow cytometry
- ANC \geq 500/ μ L and platelets \geq 75,000/ μ L without transfusions
- No evidence of extramedullary disease

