8.1.3 Partial response (PR)

- Bone marrow with 5% to 25% blasts by flow cytometry and a decrease of at least 50% in blast percentage
- No evidence of extramedullary disease

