8.1.4 No response (NR)

Participant fails to qualify for any of the categories listed above

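### The Phase II success definition lets patients enrolled with under 5% blasts count as CR or CRi on a marrow criterion they already met at entry

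*Combined protocol and SAP*

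**What the plan says.** **Entry.** Section 3.1.3 requires at least 5% blasts "and/or increasing levels of MRD in the bone marrow as assessed by flow cytometry". A patient can therefore enrol on rising MRD with fewer than 5% blasts.

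**Response criteria.** The marrow condition for CR in Section 8.1.1 is "Bone marrow with < 5% blasts confirmed by flow cytometry", and CRi in 8.1.2 uses the same one. Both also require no extramedullary disease. The ANC and platelet thresholds only separate CR from CRi. PR in 8.1.3 needs 5–25% blasts and "a decrease of at least 50% in blast percentage". NR in 8.1.4 is what remains: "Participant fails to qualify for any of the categories listed above".

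**Phase II success.** In Section 12.3, "we define a success as complete remission, complete remission with incomplete count recovery, or, for patients who are enrolled with <5% blasts", MRD negativity by the end of one course counts as success. The stage-1 rule in the same section shortens this to "8 or more successes (CR or CRi or MRD negativity) among the first 28 patients". Section 12.4 ties the final rule, 16 or more of 39, to the 12.3 definition.

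**Objective and secondary rates.** Section 1.1.2 reads "To estimate the overall response rate, as defined by complete response or complete response with incomplete count recovery", and Section 12.0 uses the same endpoint with the 30% null. Section 12.4 adds a CR rate and an overall response rate that includes PR. None of these mentions MRD.

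**The concern.** CR and CRi describe a state and not a change, and an MRD-only entrant without extramedullary disease is already in that state. Section 12.3 has a clause for this group but does not say that MRD negativity replaces CR/CRi for them. A patient whose MRD never clears could therefore count toward the 8-of-28 and 16-of-39 thresholds and toward the CR and overall response rates. The error runs in one direction only, in favour of the regimen, and the design's error rates assume it does not occur.

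**Working it through.** **Step 1: follow one patient through the text.** Take an entrant with rising MRD, under 5% blasts and no extramedullary disease, whose marrow is unchanged at the end of cycle 1.

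- CR or CRi: the blast and extramedullary conditions are met, and the counts decide which of the two applies.
- PR: not available, because it needs 5–25% blasts. It also carries a baseline condition, which CR and CRi lack.
- NR: not available, because the patient fits a category above it.
- Residual MRD does not remove the label. Section 4.1 refers to patients with "CR or CRi status (as defined in Section 8.1) at day 15 (regardless of MRD status".
- Section 12.3: MRD negativity is not reached, but CR or CRi is, and nothing there excludes it. The patient is scored as a success.

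**Step 2: reproduce the plan's figures.** Inputs from 12.3 and 12.4: continue if at least 8 of 28, add 11, and declare the therapy worthy of further study if at least 16 of 39.

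P(go | p) = Σ over x = 8…28 of Bin(x; 28, p) × P[Bin(11, p) ≥ 16 − x]

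- p = 0.30: 0.0943 (plan: 10%)
- p = 0.50: 0.9001 (plan: 90%)

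The design is correct for whatever rate is being counted.

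**Step 3: effect of automatic credit.** Let f be the share of MRD-only entrants and q the total share of them scored as successes, genuine plus automatic. Neither is in the documents, so both are assumptions. Assume true success is 30% in everyone (for MRD-only patients, 30% reach MRD negativity). The scored rate is

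p = (1 − f) × 0.30 + f × q

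If a share c of MRD-only non-responders is credited, q = 0.30 + 0.70c. So q = 0.60 means c = 0.43, and q = 1.00 means c = 1.

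| f | p (q = 0.60 to 1.00) | P(go), true rate 30% |
|---|---|---|
| 0 | 0.300 | 9.4% |
| 2% | 0.306–0.314 | 11–13% |
| 5% | 0.315–0.335 | 13–20% |
| 10% | 0.330–0.370 | 18–36% |
| 20% | 0.360–0.440 | 31–70% |

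For example, f = 10% and q = 1.00 gives p = 0.90 × 0.30 + 0.10 × 1.00 = 0.37, and P(go) = 0.357.

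At lighter credit, q = 0.40, P(go) is 9.9%, 10.7%, 12.0% and 15.0% for f = 2%, 5%, 10% and 20%.

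**Step 4: the same in patient counts.** With k of 39 MRD-only patients all credited, the other patients at 30% and the k patients falling at random across the two stages, P(go) is 0.137 for k = 1, 0.193 for k = 2 and 0.348 for k = 4.

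**The case against.** The strongest reply is intent. A clause written for patients enrolled with under 5% blasts would do almost nothing if CR/CRi also counted for them, and a state present at entry is not something a patient achieves. The stage-1 parenthesis is shorthand for a term just defined, and the Section 4.1 wording concerns transplant decisions, not endpoint scoring. On this reading the false-go probability is 9.4% at any f.

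The reply stands as a statement of what Section 12.3 probably means. But that meaning is not written down, and a go/no-go rule should not rest on inference. It also cannot help Sections 1.1.2 and 12.0 or the CR and overall response rates in 12.4, which have no MRD clause to interpret.

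Four lesser points stand as limits:
- q = 1.00 is a ceiling: some non-responders will progress to 5% blasts or more by evaluation, and deaths count as failures.
- The 0.60 floor for q is a choice, and the q = 0.40 figures show how the effect shrinks below it.
- A patient whose counts are held up only by transfusion may fit neither CR nor CRi cleanly.
- Section 8.1 gives no threshold for MRD negativity.

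None of these removes the gap.

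**Conclusion.** The concern holds and should be fixed. Followed literally, the plan scores an unchanged MRD-only entrant without extramedullary disease as a CR or CRi, and hence as a Phase II success. The design calculation itself is sound.

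The size depends on f and q, which the documents do not give, and on applying the 30% null to MRD negativity in this subgroup. There is no effect if no such patients enrol or if the probable intent is applied. One fully credited patient in 39 is enough to take the false-go probability above the stated 10%, to about 14%. The upper table entries need both a large MRD-only share and near-complete credit, and should be read as bounds.

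A smaller, label-only conflict sits alongside: overall response means CR + CRi in 1.1.2 and 12.0 but CR + CRi + PR in 12.4. It does not touch the decision rule.

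**What to change.** 1. In Section 12.3, including the stage-1 parenthesis, state that for patients enrolled with under 5% blasts success is MRD negativity only and CR/CRi cannot be scored for them. For all other patients it is CR or CRi. Define MRD negativity, and say which measurement fixes the entry blast level.
2. In Section 12.4, do not credit these patients with CR or overall response on the blast criterion alone. Either report those rates among patients with at least 5% blasts at entry, or score the others by MRD negativity.
3. Align Sections 1.1.2 and 12.0 with the 12.3 definition, and attach the 30% null to that definition only.
4. Give CR + CRi + PR in Section 12.4 a different name.

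**Cost.** Wording in 12.3, 12.4, 1.1.2 and 12.0. The 28/39 design, its 9.4% error and its 90.0% power are unchanged. No tests are added, because MRD is already required at baseline (Section 6.1) and from Day 15 on (Appendix V). The observed success rate may be lower than under the literal reading, by f × (q − 0.30): for q from 0.60 to 1.00, that is 0.6–1.4 percentage points at f = 2%, 1.5–3.5 at 5%, 3–7 at 10% and 6–14 at 20%. If 12.4 is limited to patients with at least 5% blasts at entry, the denominator of those secondary rates shrinks.

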Fludarabine and cytarabine may be given before Day 16 if the treating physician, after consulting with the principal investigator (PI), believes it is in the patient's best interest based on disease progression. In general, the fludarabine/cytarabine combination should begin prior to day 16 if the leukocyte count is greater than 50,000/ μ l and increases by >50%. For example, if the leukocyte count is 30,000/ μ l and increases to 46,000/ μ l, fludarabine and cytarabine will start on day 16 as planned. However, if the leukocyte count is 60,000/ μ l and increases to 91,000/ μ l, fludarabine and cytarabine may be started early.

Note that these are guidelines that should be used in the context of each patient's clinical condition.

If fludarabine and cytarabine are given prior to Day 16, the administration of selinexor should be held at start of fludarabine and cytarabine administration and resumed 3 days after completion of fludarabine and cytarabine to complete total of three weeks of selinexor during course one.

Diagnostic lumbar puncture and **intrathecal (IT) chemotherapy** should be given prior to cycle 1, but may be delayed if clinically indicated. IT cytarabine, IT methotrexate, and IT methotrexate/ hydrocortisone/cytarabine (MHA) are all acceptable. Note that the first dose of IT chemotherapy may be given prior to or after enrollment on SELHEM.

Patients without evidence of central nervous system (CNS) leukemia will receive no further IT therapy during cycle 1. Patients with CNS disease (defined as the presence of any blasts in the CSF) will receive weekly ITMHA until the cerebrospinal fluid becomes free of leukemia.

For patients who require IT therapy on day 15, administration of IT therapy should be separated from administration of IV fludarabine and cytarabine by at least one day.

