6.0 REQUIRED EVALUATIONS, TESTS, OBSERVATIONS

6.1 Pre-Treatment Clinical Evaluations

- Complete medical history
- Physical exam with vital signs
- Height, weight, BSA
- Complete blood count with differential*
- Chemistry profile: glucose, electrolytes, BUN, creatinine, LDH, uric acid, bilirubin, SGOT, SGPT, calcium, phosphorous, magnesium, total protein and albumin*
- Coagulation screen*
- HLA typing, if not done previously
- Chest x-ray*
- EKG, echocardiogram*
- Lumbar puncture with CSF cell count and cytology.
- Ophthalmic exam (preferably prior to first dose of selinexor, but may be obtained within one week of dose #1).
- Serum pregnancy test of females of childbearing potential
- Bone marrow evaluation for morphology, immunophenotyping, cytogenetics, molecular diagnosis, minimal residual disease (MRD), and tissue banking*. Morphologic examination and MRD are required for all patients. Immunophenotyping, cytogenetic analysis, and molecular analysis should be performed as clinically indicated (e.g., if not done at the time of relapse). For patients with elevated leukocyte counts and high blast percentages, and patients too ill to undergo bone marrow aspirate, all diagnostic studies may be performed on blood rather than bone marrow. MRD studies must be performed centrally at St. Jude, whereas other diagnostic studies may be performed locally as desired by the treating physician.

** Complete blood count and chemistry profile should be performed within 48 hours of first dose of selinexor. Chest x-ray, EKG, and echocardiogram should be performed within 2 weeks of first dose of selinexor. Tissue banking applies to participants who have signed St. Jude TBANK consent only. TBANK is an optional protocol for collaborating sites.*

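### The MRD-negativity route to Phase II success omits the extramedullary-disease condition that CR, CRi and PR all carry, so a non-responder under Section 8.1 can count as a success

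*Combined protocol and SAP*

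**What the plan says.** **Success definition (12.3).** Success is CR, CRi or, "for patients who are enrolled with <5% blasts, the achievement of MRD negativity, by the end of one course of therapy". The stage 1 stopping rule in the same section lists MRD negativity in a parenthesis beside CR and CRi, with no qualification. The trial continues with 8 or more successes among 28 patients. Section 12.4 calls the therapy worthy of further study with 16 or more among 39.

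**Response criteria (8.1).** CR (8.1.1), CRi (8.1.2) and PR (8.1.3) each carry the condition "No evidence of extramedullary disease". A patient who meets none of them is No response (8.1.4). New extramedullary disease after CR is, by itself, relapse (8.1.5). MRD negativity is not a category in 8.1, and I found no numerical threshold for it in 8.1, 12.3, 6.1 or Appendix V.

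**Entry (3.1.3).** Patients need at least 5% "leukemic blasts in the bone marrow and/or increasing levels of MRD in the bone marrow as assessed by flow cytometry". Patients without an adequate marrow sample may enter on blood evidence. Section 3.2 does not list extramedullary leukemia as an exclusion. Section 4.1 states: "Patients with CNS disease (defined as the presence of any blasts in the CSF) will receive weekly ITMHA".

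**MRD testing.** Section 6.1 says "Morphologic examination and MRD are required for all patients" at baseline and "MRD studies must be performed centrally at St. Jude". Appendix V sends marrow for MRD to the same institution from Day 15 onward.

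**The concern.** The MRD route exists because a patient who enters with fewer than 5% blasts already meets the marrow criterion for remission and needs a different test of benefit. As written, it replaces the marrow criterion and also drops the extramedullary criterion. Two patients who both finish with persisting extramedullary leukemia are then scored differently: the one who entered with 5% blasts or more fails, while the one who entered at MRD level and cleared the marrow succeeds.

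This is the primary endpoint of a single-arm trial whose decision is a count. Compared with the same route carrying the condition, the omission can only add successes, so it moves the result only toward a go. It also makes the documents disagree on one patient: a success in 12.3, but a non-responder in the CR and overall response rates of 12.4, which rest on 8.1.

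**Working it through.** **Step 1: can the patient exist under the text?** Take a patient with fewer than 5% marrow blasts, rising marrow MRD and extramedullary disease (for example, blasts in the CSF) at entry. After one course the marrow is MRD-negative and the extramedullary disease persists.

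| Rule | Outcome for this patient |
|---|---|
| Entry, 3.1.3 | Eligible through rising MRD |
| Exclusions, 3.2 | Extramedullary disease not listed |
| 4.1 | CNS disease provided for |
| CR, CRi, PR (8.1.1–8.1.3) | Not met: extramedullary disease present |
| 8.1.4 | No response |
| 12.3, MRD route | Success |

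The last two rows conflict. The conflict does not depend on the MRD threshold. It also remains whether or not patients with fewer than 5% blasts may use the CR/CRi route, because this patient fails that route in any case.

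**Step 2: reproduce the design.** Inputs from 12.3 and 12.4: n1 = 28, continue at 8 or more; N = 39, go at 16 or more; null 30%, alternative 50%. With X1 ~ Bin(28, p) and X2 ~ Bin(11, p),

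P(go) = Σ over x = 8 to 28 of P(X1 = x) · P(X2 ≥ 16 − x).

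At p = 0.30, P(go) = 0.0943; at p = 0.50, P(go) = 0.9001. An exhaustive minimax search at 30% versus 50%, with both error limits at 10%, returns the same design. The stated 10% is the design limit, and the exact error lies within it. The design is sound.

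**Step 3: effect at the boundary.** One patient is 1/39 = 2.6 percentage points. 15/39 = 38.5% is a no-go and 16/39 = 41.0% is a go. Likewise 7/28 stops the trial and 8/28 continues it.

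**Step 4: illustration under assumptions.** Suppose every patient has a 30% chance of success under the intended definition, and the loose wording raises this chance to s for k patients enrolled in stage 1. Then X1 = Bin(28 − k, 0.30) + Bin(k, s), and the rest is as in Step 2. Both k and s are assumptions; the documents give neither.

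| Assumed s | k = 0 | k = 1 | k = 2 | k = 3 |
|---|---|---|---|---|
| 0.40 | 0.0943 | 0.1004 | 0.1068 | 0.1134 |
| 0.50 | 0.0943 | 0.1065 | 0.1197 | 0.1341 |
| 1.00 (worst case) | 0.0943 | 0.1369 | 0.1929 | 0.2635 |

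Hand check for k = 1: P(go) is linear in s, so at s = 0.50 it is 0.0943 + (0.20/0.70) × (0.1369 − 0.0943) = 0.1065. Placing the patients in stage 2 changes little: at s = 1.00 the values are 0.1367, 0.1922 and 0.2617.

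**The case against.** **The case is rare.** It needs fewer than 5% blasts, rising MRD, concurrent extramedullary disease, marrow clearance and extramedullary persistence after the same course. CNS disease, the extramedullary site that the plan provides for, is treated intrathecally until the CSF clears. This stands. It limits the size of the point but does not remove the contradiction.

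**The MRD route is stricter on the marrow.** A patient who enters with 5% blasts or more can succeed while still MRD-positive; an MRD-level entrant cannot succeed by the MRD route. This also stands, so the route as a whole is not simply lenient. It does not compensate for ignoring disease outside the marrow.

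**The test's own error rate is intact.** Section 12.4 applies the 30% null to success as 12.3 defines it. That is correct. A reader might infer from the table that the trial's type I error is really 26%. The documents do not support this: the figures measure a go against a success definition that excludes persisting extramedullary disease. The bottom row also assumes certain successes, whereas these patients must still clear marrow MRD.

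**A stronger reading of the missing cut-off.** A reader might infer that patients can enter already MRD-negative and count as successes from the start. The text points the other way. Entry on a marrow sample with fewer than 5% blasts requires "increasing levels of MRD in the bone marrow as assessed by flow cytometry", so MRD must be detectable. Section 12.3 speaks of achieving negativity, which in ordinary use means conversion. Baseline and later MRD go to the same institution. The gap opens only if the threshold applied later lies above the entry value, or if no baseline marrow value exists because the patient entered under "If an adequate bone marrow sample cannot be obtained, patients may be enrolled if there is unequivocal evidence of leukemia in the peripheral blood". The text does not bar these cases, but nothing suggests that they are expected. The missing threshold is mainly missing detail, and a strict threshold could also cost successes.

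**Conclusion.** The inconsistency is real and lies in the primary endpoint: 12.3 scores as a success a patient whom 8.1.4 calls No response. That conclusion rests on the text alone. Its size cannot be fixed from the documents and is probably small. One mis-scored patient can decide the result at 15 versus 16 of 39. Under the stated assumptions, one to three affected patients raise the go probability from 9.4% to 10.6%, 12.0% and 13.4% at a 50% chance each. The worst case of certain successes gives 13.7%, 19.3% and 26.3%. These are illustrations, not predictions. The undefined MRD threshold deserves a clarifying sentence but is secondary.

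**What to change.** 1. In 12.3, extend the MRD route so that patients enrolled with fewer than 5% blasts need MRD negativity together with "No evidence of extramedullary disease", the condition used in 8.1.1. Make the same change in the stopping-rule parenthesis.
2. In 8.1, state the central laboratory's threshold for MRD negativity, and say that achieving it means conversion from a baseline value at or above that threshold. State that patients who enter below it stay in the denominator.

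The cost is a few sentences. Baseline and follow-up MRD are already required, and CR and CRi already need a judgment on extramedullary disease, so the endpoint calls for no new kind of assessment. The sample size and the cut-offs of 8/28 and 16/39 do not change. The observed success rate may fall slightly, and any sub-threshold entrant kept in the denominator could not succeed by the MRD route.
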